Data Structure: There are two key unique features of the primary data for this proposal. First, because couples are enrolled in the study, there is inherent nesting of two individuals within each couple. Second, the measurement design leads to repeated measurements outcomes for some of the aims. Given the aims of the study, many of the outcomes will be evaluated using descriptive statistics. However, issues such as nesting and repeated measurements will be carefully considered. For example, for the first aim, uptake will be reported by each individual within the couple, and the descriptive statistics will be reported both at the individual level within the couple and at the aggregate couple level. For the outcomes that will be evaluated using inferential statistical analyses, the nested data structures (e.g., repeated measurements within couples) will be addressed using mixed-effects regression models (MRMs; e.g.).⁸¹ These highly flexible models accommodate variability in the number/spacing of outcome measurements, and they readily accommodate linear and non-linear outcome distributions (e.g., dichotomous, count). **Outcome Distributions & Individual Trajectories:** Prior to analysis, each outcome will be carefully inspected to determine the most appropriate distribution for modeling. Likewise, for outcomes with repeated measurements, the trajectory for each participant on each outcome will be plotted using “spaghetti plots”.⁸² These plots will illustrate the level of and variability in each outcome, along with patterns of change over time. **Model Building & Estimation:** Singer and Willett’s (2003)⁸³ model building approach will be used to specify fixed and random effects. The MRMs will be performed using MLwiN software.⁸⁴ Due to the relatively modest sample size for some of the analyses, the models will also be performed using Bayesian MCMC-based estimation⁸⁵ in MLwiN. This simulation-based approach utilizes a large number of iterations – each informing the next – to produce an empirically-based sampling distribution for each parameter. For example, rather than a single point estimate of the parameter of interest, the MCMC-based provides the magnitude, precision, and variability of the parameter estimates. **Attrition & Missing Data:** Individuals or couples who drop out of clinic care will be retained, when possible, in ongoing research measurement according to Intention-to-treat principles.⁸⁶ Some research data will inevitably be missing, and the methods recommended by Schafer and Graham⁸⁷ will be used to evaluate missing data assumptions and guide the subsequent analyses. Given few missing data and evidence supporting a MAR mechanism, the procedures detailed above will be utilized with all available data. Given non-trivial missing data and evidence supporting MAR, multiple imputation for longitudinal data will be used to provide complete data.⁸⁸ Finally, given non-trivial missing data and evidence suggesting NMAR, pattern mixture models will be used to control the missing data.⁸²

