AIM 3 - We hypothesize that a moderate proportion of HIV negative partners will utilize PrEP (~ 30%), that PrEP utilization among HIV negative partners will be associated with lack of ARV use by positive partners, and ARV use by positive partners will be associated with lack of PrEP use by negative partners. To evaluate the factors associated with uptake of PrEP, a single level logistic regression model with a logit link function will be performed. Demographic variables such as age and gender will be evaluated as predictors of PrEP uptake, with the results focusing on the odds ratios, and corresponding 95% confidence intervals, for these variables. To evaluate association between ARV and PrEP utilization within couples, two main models will be performed. For the first, the outcomes will be variables related to the use of PrEP. Likewise, for the second, the outcomes will be variables related to the use of ARV. These outcomes will be evaluated using MRMs as described above. Because each outcome is specific to one member of the couple (i.e., the negative partner for PrEP and the positive partner for ARV), the data will have a two level structure with repeated measurements (level-1) nested within couples (level-2). At the repeated measurements level of the model, the partner's ARV or PrEP status for the preceding time period will be entered as a time-varying covariate. For example, for the PrEP outcome, the positive partner's ARV status will be entered at level-1, and this will test for differences in the use of PrEP for negative partners whose positive partners were on ARV versus not on ARV. Similarly, for the ARV outcome, the negative partner's PrEP status will be entered at level-1, and this will test for differences in the use of ARV for positive partners whose negative partners were on PrEP versus not on PrEP. More tailored formulations are also possible. For example, introducing a lag between the predictor and outcome could test the extent to which PrEP and ARV status were associated with later initiation of ARV or PrEP. **We hypothesize couples will alternate risk reduction strategies (abstinence, ARV treatment for the positive partner, PrEP for the negative partner, and condom use) but typically maintain at least one strategy.** Each risk reduction strategy will be considered as a separate outcome, with repeated measurements of strategies (level-1) nested within couples (level-2). The model specification will be heavily informed by preliminary evaluation of the spaghetti plots, as described above. These plots will guide tests for patterns of change over time (e.g., linear), specific phases of change, or even invariance over time such that aggregation is justified. After building the mixed-effects model, predictor variables related to the use of abstinence, condoms, ARV, or PrEP will be added to the model. These variables will also be considered for entry as time-varying covariates (i.e., entry at level-1) or as aggregative, couple-specific predictors based on the findings of the previous models. Such a formulation will test for, for example, differences in the use of risk reduction strategies for time periods when the positive partner is on ART versus not on ART. Based on the descriptive statistics and the patterns of use of each individual strategy over time, supplemental analyses will be considered that simultaneously evaluate all of the strategies. For instance, cluster analyses could be used to identify groupings of individuals based on the combination of risk reduction strategies utilized.

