For AIM 2 - For the estimated sub-sample of 50 individuals for the PrEP use outcome, the 95% confidence interval for 50% PrEP use is 36% to 64%. If this percentage is as high as 75%, the confidence interval would be 63% to 87%. For the MRMs, this sample is sufficient for accurate estimates of fixed effects.⁸⁹ Although the point estimates of variance components and SEs could be biased, the proposed Bayesian MCMC-based analyses will provide increasingly valid estimates and will provide information about the variability and precision of the estimates.⁸⁵ Also of note, with the current design, the primary statistical test (i.e., that a time-varying correlation = 0) has a much smaller sample size requirement than does the primary statistical test for a traditional randomized design (i.e., between-group difference in slopes = 0). Statistical power was estimated using the method recommended by Maas and Hox⁸⁹ for a design with a level-1 predictor variable, a random intercept, and no other random effects. The lower limit on power is provided by the outcomes with 3 research measurement occasions, and outcomes utilizing clinic data and samples will offer much higher statistical power. With an estimated 50 individuals and 3 measurement occasions, the level-1 sample size is 150. Penalizing this sample for a nesting effect characteristic of repeated measurement data, ICC = .50, the effective level-1 sample size is 75 (i.e., given the dependence in the data, the level-1 sample of 150 offers the power of a sample of 75). For the dichotomous outcome and the dichotomous level-1 predictor, with an effective level-1 sample of 75, power is .80 to detect an event rate of 30%

(i.e., OR = 4.26). Assuming up to a 20% loss to follow-up rate, we will enroll 60 couples to ensure there are at least 150 measurements in total.

In sum, with between 442 and 1,000 couples in the HIV self-testing component of the study, and between 60-70 couples in the Dyadic Care component of the study we estimate that we will have adequate statistical precision and power to answer the requisite study questions.

TIMELINE – Based on experience working in the area we feel confident we can meet these goals:

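### Aim 3 enters the partner's ARV or PrEP status as a single covariate, so its coefficient blends change within couples with differences between couples and can mask substitution when only three survey occasions are used

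*Combined protocol and SAP*

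**What the plan says.** Under Evaluation of Specific Aims & Associated Hypotheses, AIM 3, the hypothesis is that "PrEP utilization among HIV negative partners will be associated with lack of ARV use by positive partners", and the converse for ARV use. Two mixed models test it, one with PrEP use and one with ARV use as the outcome. For both, "the data will have a two level structure with repeated measurements (level-1) nested within couples (level-2"). In each, the partner's "status for the preceding time period will be entered as a time-varying covariate". Neither centring nor a couple-mean term is mentioned.

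The target is worded in two ways. The Aim 3 text says that the PrEP model tests "differences in the use of PrEP for negative partners whose positive partners were on ARV versus not on ARV", which reads as a comparison between couples. The later Aim 3 models of risk-reduction strategies look for "differences in the use of risk reduction strategies for time periods when the positive partner is on ART versus not on ART", which reads as change over time. Aim 3(b) in the list of specific aims asks how treatment of one partner affects PrEP use by the other, and the reverse.

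Precision of Estimates and Statistical Power, in its Aim 2 paragraph, refers to "the primary statistical test (i.e., that a time-varying correlation = 0"), and bases power on "a design with a level-1 predictor variable, a random intercept, and no other random effects". The Analysis Plan leaves room for other choices: a published "model building approach will be used to specify fixed and random effects".

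**The concern.** In a random-intercept model, one uncentred time-varying covariate has one coefficient for two associations. The first is within couples: does a negative partner use PrEP more in periods when the positive partner is off ARV? The second is between couples: do couples with more ARV use also use more PrEP? The Aim 3 hypothesis is one of substitution, so the first should be negative. The second may well be positive, because couples who engage well with services may use both.

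The design makes such stable differences plausible. Couples come both from household self-testing and from patients already in care at the CTC. The section on enrolment in care as a couple makes treatment eligibility independent of CD4 count, so ARV status may change little within a couple, and the between-couple part then carries most weight. A null Aim 3 result could mean no substitution, or substitution masked by engagement, and the planned model could not tell these apart.

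**Working it through.** **1. The plan's own power figure.** Inputs from the power section: 50 individuals, 3 occasions, ICC 0.50. Effective size = 150 / [1 + (3 − 1) × 0.50] = 75, as stated. The base rates behind power .80 at OR 4.26 are not given. With alpha 0.05 two-sided (assumed) and 37.5 per group, 50% against 81% gives power 0.819, and an overall event rate of 30% (15.7% against 44.3%) gives 0.781. The figure is reproduced approximately. This design effect suits a predictor that is constant within a couple, so it does not describe a within-couple test.

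**2. Weight of the between-couple part.** For a linear random-intercept model with T occasions and persistence ρ of the partner's status (assumed):

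weight = ψB / (W + ψB), with ψ = (1 − ICC) / (1 − ICC + T × ICC), W = (T − 1)(1 − ρ), B = 1 + (T − 1)ρ.

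At T = 3 and ICC 0.50, ψ = 0.5 / 2.0 = 0.25. At ρ = 0.8, W = 0.4, B = 2.6, ψB = 0.65, and the weight is 0.65 / 1.05 = 62%. It is 33% at ρ = 0.5 and 78% at ρ = 0.9. At T = 18 the same three values of ρ give 6%, 18% and 34%.

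Take a within-couple OR of 1/4.26 = 0.235, log-odds −1.449. At T = 3 and ρ = 0.8, a between-couple log-odds of 1.449 × 0.381 / 0.619 = 0.89, or OR 2.4, brings the blended coefficient to zero. At ρ = 0.9, an OR of about 1.5 is enough.

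**3. Simulation at the plan's size.** Random-intercept logistic models, 50 couples × 3 occasions, latent ICC 0.50, true within-couple OR 0.235, 400 runs per scenario. Ranges cover two settings for the spread of the couple-level ARV propensity (1.5 and 3.0). Simulated PrEP use was near 50%, not the 30% expected in Aim 3.

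| Couple-level correlation (assumed) | Single-term OR (median) | Single term significantly negative | Within-couple OR (median) | Within-couple term significantly negative |
|---|---|---|---|---|
| 0 | 0.23–0.24 | 0.72–0.74 | 0.23 | 0.43–0.56 |
| 0.3 | 0.34–0.39 | 0.34–0.47 | 0.22–0.23 | 0.45–0.55 |
| 0.6 | 0.46–0.66 | 0.10–0.24 | 0.23 | 0.46–0.60 |
| 0.9 | 0.67–1.34 | 0.01–0.07 | 0.22 | 0.51–0.66 |

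The value 1.34 arises only with correlation 0.9 and the more persistent status. There the estimate exceeds 1 in 67% of runs, significantly so in 15%. With 18 occasions (3,000 couples) the single-term OR is 0.24–0.37 against 0.235, with no reversal.

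**4. A second setting.** With true within-couple OR 0.33 and 3 occasions, correlations of 0.3, 0.6 and 0.9 give single-term ORs of 0.45, 0.73 and 1.14. With 18 occasions the range is 0.41 to 0.47.

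**5. Two-way influence.** Aim 3(b) expects influence in both directions. With 3 occasions, no couple-level correlation, a true within-couple OR of 1.0 and feedback from outcome to later partner status, the within-couple term gave OR 1.25 to 1.30 in two separate runs; the single term gave 0.99 in one of these. With a true OR of 0.33 and feedback, the within-couple OR was 0.44 at zero correlation. At correlations of 0.3 or more it was 0.37–0.43, closer to the truth than the single term (0.43–1.08).

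**The case against.** The strongest reply is that the plan never says that the target is purely within couples. One Aim 3 sentence compares different couples, and for that question a positive coefficient would be an answer, not an error. This stands as far as it goes: the target is not fixed. But the aim's causal wording, the hypothesis that couples alternate strategies, and the reference to a time-varying correlation all point mainly to change over time, and one coefficient cannot answer both questions.

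A second reply is that the study is exploratory and leaves the specification open. The absence of centring is indeed inferred from silence. Yet none of the options named would separate the two parts. The tailored formulation offered as an example is a lag. Couple-level aggregates appear only for the later risk-strategy models, as an alternative to the time-varying term. A random slope does not separate the effects either.

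A third reply concerns the remedy. With no couple-level correlation, the within-couple term has power 0.43–0.56 against 0.72–0.74 for the single term. If ARV use were about 89% (an assumption), only about 4 of 50 couples would show change in both ARV and PrEP over three occasions. Feedback biases the within-couple term as well. All of this stands, and it rules out replacing the planned estimate outright.

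A reader might also infer that this is the study's declared primary test. The phrase sits in the Aim 2 power paragraph and contrasts types of design; tying it to the Aim 3 models is an inference.

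**Conclusion.** The concern holds as one of blending and likely attenuation. With three survey occasions and couple-level correlations of 0.3 to 0.9, a true within-couple OR of 0.33 appears as about 0.45 to 1.14. With 18 monthly records it appears as about 0.41 to 0.47, which is modest. The plan gives 18 monthly measurements for the Aim 2 refill outcome and does not say which records will serve the Aim 3 models. It names three-occasion outcomes as its lower limit on power.

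A reader might infer that the planned model will reverse the sign. The documents do not support that. They give neither the couple-level correlation nor the persistence of status, and reversal appeared only with three occasions and correlations of about 0.9 or above. If one shared trait drives both partners' use (correlation 1.0), the single-term OR is 0.61, 1.02 and 1.76 at log-odds loadings of 1.0, 1.5 and 2.0; a repeat gave 0.62, 1.06 and 1.65. That is a worst case, not an expectation.

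**What to change.** State that Aim 3(b) targets within-couple change. In each of the two main Aim 3 models, enter the partner's preceding-period status as two terms: its deviation from the couple's own mean, and the couple mean. Report both coefficients beside the planned single-term estimate. Read the within-couple term as the evidence on substitution, without making it the sole test. Apply the same split wherever ARV or PrEP status is a time-varying predictor in the later risk-strategy models.

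State whether three-occasion survey data or monthly records will be used, and report how many couples change status. Acknowledge three limits: less precision when few couples change, a power statement that does not describe the within-couple term, and bias in that term with three occasions if ARV and PrEP use influence each other. The cost is one extra model term and some reporting, with no new data collection.

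### Aim 3 hypothesises that couples alternate strategies, but models each strategy's change over time separately, defines no within-couple switching outcome, and does not require invariance to hold within couples before aggregating

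*Combined protocol and SAP*

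**What the plan says.** Under Evaluation of Specific Aims, AIM 3, the hypothesis reads "We hypothesize couples will alternate risk reduction strategies", with the qualification that couples will usually keep at least one going. The strategies are abstinence, ARV, PrEP and condoms. The planned structure is one model per strategy ("Each risk reduction strategy will be considered as a separate outcome, with repeated measurements of strategies (level-1) nested within couples (level-2").

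On choosing the model, the same section says: "The model specification will be heavily informed by preliminary evaluation of the spaghetti plots, as described above". The plots are to guide tests for patterns such as a linear trend, "specific phases of change, or even invariance over time such that aggregation is justified". The other strategies are then added as predictors, either time-varying "or as aggregative, couple-specific predictors based on the findings of the previous models". An analysis of all strategies together is something to be considered, with clustering as an example.

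The Analysis Plan's paragraph on outcome distributions and trajectories defines the plots: "the trajectory for each participant on each outcome will be plotted using" spaghetti plots. Their purpose is also stated: "These plots will illustrate the level of and variability in each outcome, along with patterns of change over time".

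No passage defines a switch, a transition, or an indicator that a couple is using at least one strategy. No criterion is given for invariance, nor is it said whether invariance refers to the couple or to the average.

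**The concern.** Both halves of the hypothesis describe the set of strategies a couple holds and how that set changes. The planned outcomes describe one strategy at a time. A trend or phase effect in one strategy's model answers whether use of that strategy rises or falls, which is a different question from whether couples swap one strategy for another.

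The aggregation clause adds to this. If a flat average were read as invariance, use would be averaged over time and within-couple switching would disappear from the data. Aim 3(c) asks for patterns of strategy use over time, and section B lists those patterns among the study's innovations. A report of stable use could then be written about couples who are switching, or a report of change about couples who only added a strategy.

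**Working it through.** **The plan's own figures.** None is given for the alternation hypothesis. The nearest is the effective sample size under Precision of Estimates and Statistical Power, AIM 2: 50 individuals × 3 occasions = 150, design effect 1 + (3 − 1) × 0.50 = 2, and 150 / 2 = 75, as stated. It concerns a time-varying predictor and does not bear on switching.

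**Inputs.** Surveys at baseline, 6, 12 and 18 months (opening description of the second part of the study); three occasions in the power section; expected PrEP use of about 30% (AIM 3). The documents give no switching rates, so every flow and pattern below is assumed.

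**1. A flat average with switching.** Let p be the proportion using a strategy, s the proportion of users who stop in an interval, and a the proportion of non-users who start.

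- Next visit: p′ = p(1 − s) + (1 − p)a. Use is flat when ps = (1 − p)a.
- Couples changing status: ps + (1 − p)a.
- With p = 0.30, s = 0.70, a = 0.30: p′ = 0.30 × 0.30 + 0.70 × 0.30 = 0.09 + 0.21 = 0.30.
- Couples changing: 0.30 × 0.70 + 0.70 × 0.30 = 0.21 + 0.21 = 0.42.

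Use stays at 30% while 42% of couples change in each interval.

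**2. A moving average without alternation.** If 30% of couples start PrEP after baseline and keep it, mean use over three visits is 0, 0.30, 0.30. No couple has replaced one strategy with another.

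**3. When switching does move the average.** If every couple switches from a 60/40 split, use goes from 0.60 to 0.40. The cancellation in step 1 needs balanced flows.

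**4. What each summary sees (three visits, use coded 0/1).**

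| Pattern | Mean by visit | Couples whose own line changes | Couple slopes |
|---|---|---|---|
| Half always on, half always off | 0.50, 0.50, 0.50 | 0% | 0 |
| Half 0-1-0, half 1-0-1 | 0.50, 0.50, 0.50 | 100% | 0 |
| One switch each, directions balanced | 0.50, 0.50, 0.50 | 100% | ±0.50 |

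The means cannot separate the rows; the couples' own lines can. A random linear slope helps only in part. For 0-1-0 the slope is (−1 × 0 + 0 × 1 + 1 × 0) / 2 = 0, the same as for a stable couple. With four visits, 0-1-0-1 gives (−0.5 + 1.5) / 5 = 0.20.

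**5. The at-least-one half.** Take two strategies, each with mean use 0.50 at every visit. If they replace each other, 100% of couples use at least one. If the same couples use both at the same visits, 50% do. Separate models of the two averages do not distinguish these cases.

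**6. Precision of a direct estimate.** For a proportion of 50% in 50 couples the 95% CI is 0.50 ± 1.96 × √(0.25 / 50) = 0.50 ± 0.139, or 36% to 64%. This is the interval the plan already quotes for PrEP use. With 60 couples it is 0.50 ± 0.127, or 37% to 63%.

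**The case against.** A reader might infer that the plan contains a rule declaring alternating couples invariant, and might attach an error rate to it. The documents do not support that.

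- The basis for choosing the model is one trajectory per participant. Couples switching in opposite directions give crossing lines, and step 4 shows that individual lines separate switchers from stable couples completely.
- No test, significance level or threshold for aggregation is stated. Any percentage of cohorts misclassified, or of real declines missed, would describe a decision rule supplied by the reader.
- The phrase "a random intercept, and no other random effects" belongs to a power method printed under AIM 2. The Analysis Plan leaves random effects to be specified by model building, so the phrase does not show that the Aim 3 models concern only an average trajectory.
- Time-varying entry of the other strategies is offered alongside aggregated entry. Lagged PrEP and ARV models and a joint analysis are also mentioned. Where two strategies replace each other exactly, their within-couple correlation is −1.0, which time-varying entry could show.
- Exact balance is implausible for PrEP from baseline. The Alternatives section says PrEP is unavailable in Tanzania outside research projects, so baseline use should be near zero and uptake will move the average.

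All of this stands against the stronger reading. It does not supply the missing estimate. A plot with no criterion is not a result, and if use is coded 0/1 only 2³ = 8 paths exist with three visits (2⁴ = 16 with four), so some 50 couples' lines will overprint. The covariate and joint analyses are only to be considered, and neither counts transitions. AIM 3 also says this formulation will compare periods on and off ART, which a couple-level average cannot do.

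**Conclusion.** The concern holds as a gap between hypothesis and analysis. Aim 3 states an alternation hypothesis and an at-least-one-strategy hypothesis, and the plan gives a direct estimate of neither. Tests of change in each strategy's average do not fill the gap: the average can be flat with 42% of couples changing per interval, or rise from 0 to 30% with none alternating. Those sizes rest on assumed flows and show what is possible, not what is expected. The flat case applies to PrEP only after baseline.

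The aggregation clause is ambiguous rather than wrong. It would be sound if invariance meant constant use within each couple; the plan does not say so, which leaves a flat average open as a justification. Because aggregation is legitimate when couples' own lines are constant, a blanket ban would go too far. The study is exploratory, so this is a worthwhile improvement to the plan rather than a flaw that invalidates it.

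**What to change.** 1. Make within-couple switching the endpoint for the alternation hypothesis. For each couple and each adjacent pair of visits (three pairs across the four surveys), code whether the set of strategies changed and how: dropped, added or replaced. Report the proportion of couples with at least one replacement, with a 95% CI, and the visit-to-visit transition table.
2. At each visit, report the proportion of couples using at least one strategy, with a 95% CI.
3. State that aggregation over time is allowed only where use is constant within couples, and not because the average is flat or a time effect is non-significant. Otherwise enter the other strategies as time-varying covariates.

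The cost is plan wording and one or two derived variables from surveys already scheduled. The intervals will be wide (step 6). Switches that occur and reverse between surveys will still be missed for strategies measured only by survey, such as condom use and abstinence. ARV refills are recorded monthly and PrEP refills are tracked in the clinical records, so those two are less exposed.
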